### 6.2.2. Adverse Events Definition and Reporting

#### Medical Monitoring

Data will be collected by monthly clinic appointments for the first 3 months. All study patients will have direct access to study personnel via a dedicated cellular phone.

#### Definition and Classification of Adverse Events

Adverse events will include medication side effects including nausea, vomiting, diarrhea, rash, itching, hypotension, and thromboembolic events.

**Data Collection for Adverse Events**

Adverse events will be noted in each participant's file. Their responses to the biweekly phone calls and monthly clinic visits about new symptoms related to the study medication will be reviewed and followed up promptly.

Adverse events will be grading according to the following scale:

- Mild: An experience that is transient and requires no special treatment or intervention. The experience does not generally interfere with usual daily activities.
- Moderate: An experience that is alleviated with simple therapeutic treatments. The experience impacts usual daily activities.
- Severe: An experience that require therapeutic intervention. The experience interrupts usual daily activities. If hospitalization (or prolongation of hospitalization) is required for treatment, it becomes a severe adverse event.

Each adverse event will be assessed and determine to be related or not related to the study medication.

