### 4.3 Secondary Objectives (if applicable)

To determine the need for hospitalization for symptomatic anemia or acute gastrointestinal bleed

To determine the need for additional endoscopic interventions

To determine the rate of clinically significant side effects associated with TXA therapy leading to drug withdrawal

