### **6.3.6 Removal of subjects**

- At the time of consent, participants will be informed that their participation in this research study is voluntary and they may discontinue participation without penalty at any time.
- Subjects will be withdrawn from the study by the investigator if they are to have serious adverse reactions to TXA or to protect the subjects from excessive risk due to lack of benefit demonstrated by TXA.
- Data collection prior to participant withdrawal may be retained and used in a manner that is consistent with study design and purpose unless participant expresses that their information to not used in the study

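### Section 6.2.2 gives no cause-independent adverse event definition and makes hospitalization a severity criterion, while 6.3.6 relies on the undefined term *serious*

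*Combined protocol and SAP*

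**What the plan says.** Under *Definition and Classification of Adverse Events*, section 6.2.2 has a single sentence: "Adverse events will include medication side effects including nausea, vomiting, diarrhea, rash, itching, hypotension, and thromboembolic events". Section 3.3.1 (Potential Risks) carries the same sentence.

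Under *Data Collection for Adverse Events*, events are to be noted in the participant's file, and answers given at phone calls and clinic visits "about new symptoms related to the study medication will be reviewed and followed up promptly". A three-step scale follows. The treatment part of the middle grade reads "Moderate: An experience that is alleviated with simple therapeutic treatments" and that of the top grade "Severe: An experience that require therapeutic intervention". The top grade ends with "If hospitalization (or prolongation of hospitalization) is required for treatment, it becomes a severe adverse event". The subsection closes with a causality step: "Each adverse event will be assessed and determine to be related or not related to the study medication".

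Section 6.3.6 uses a different word: "Subjects will be withdrawn from the study by the investigator if they are to have serious adverse reactions to TXA". The safety objective in 4.3 uses yet another: "To determine the rate of clinically significant side effects associated with TXA therapy leading to drug withdrawal".

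**The concern.** A safety comparison in a placebo-controlled trial needs events recorded in the same way in both arms before anyone judges their cause. Here the definition already assumes a drug effect, and the collection sentence points staff to symptoms attributed to the drug. An unexpected harm is the kind of event least likely to be attributed at first report.

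Intensity and seriousness are also different properties. A scale that moves from one to the other cannot report either cleanly. A withdrawal criterion that depends on *serious* has nothing in that scale to refer to.

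At stake are the adverse event comparison between arms, the count for the safety objective in 4.3, and consistent application of the withdrawal criterion in 6.3.6.

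**Working it through.** No arithmetic applies. The check sets the relevant places side by side.

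1. **Is there a general definition?** Adverse events are described in 3.3.1 and 6.2.2, both times as medication side effects with seven named items. No sentence extends the term to any medical occurrence regardless of cause. The repetition shows this is the plan's working description, not a slip in one place.

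2. **What is collected?** The 6.2.2 collection paragraph has three steps: note events in the file, review and follow up symptoms related to the medication, then class each event as related or not. The second step presupposes what the third is meant to decide. If staff follow the second step literally, few unrelated events will reach the third. If they follow the third, they need a wider definition than the one given.

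3. **Does the list cover foreseeable events?** Section 5.3.2 treats ischemic retinopathy as a contraindication to TXA, but no visual symptom is among the seven items. Whether a new visual complaint is captured would depend on someone suspecting the drug.

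4. **What does the scale measure?** Mild, moderate and severe are described mainly by need for treatment and effect on daily functioning, which is intensity. Hospitalization is then added to the top grade. A short admission for an event of low intensity becomes severe. A severe event without admission gets the same label as one with admission, so the grade does not show which events met the hospitalization criterion.

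5. **Where does *serious* appear?** It appears twice. One use is background text in 2.1 about another drug (bevacizumab). The other is the withdrawal criterion in 6.3.6. Neither comes with criteria. Section 6.2.2 has definition and reporting in its title but gives no seriousness criteria and no reporting path or timeline for serious events.

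6. **What depends on these terms?** The 4.3 safety objective combines an undefined threshold (clinical significance), a causality judgement and a withdrawal decision. Withdrawal by the investigator depends partly on *serious*. Section 7.6 also names harm from adverse events as a reason to stop the study, without saying which class of event counts.

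7. **Hospitalization for anemia or GI bleeding.** This is a secondary outcome (4.3, 5.2.2). No rule says whether such an admission is also an adverse event and, under the scale, a severe one.

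**The case against.** The strongest reply is that the text is looser than it is restrictive. The definition says events *will include* the listed effects, so the list is open. The collection paragraph starts by saying, without restriction, that adverse events are noted. The related-or-not step makes sense only if some unrelated events are recorded. All of this stands. A reader might infer that events outside the list, or thought unrelated, will definitely be lost. The documents do not support that; they support only that such events may go unrecorded, because no wider definition overrides the collection sentence.

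A reader might also infer that bleeding admissions would be missed. They would not: 5.1 monitors them separately from side effects, and 4.3 and 5.2.2 make hospitalization its own outcome. What remains is possible double listing in a safety table. Section 7.3 also continues laboratory tests and symptom reporting after a subject stops the drug, which helps capture.

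The overlap between moderate and severe is partial. Both mention treatment, but each has a second criterion on daily functioning that helps to separate them. That a clot treated without admission would be graded moderate is a hypothetical; it requires assuming that such treatment counts as simple, which the protocol does not say.

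Finally, the consent form and appendix were not available. A definition there would help, but it would still have to agree with 6.2.2 and 6.3.6.

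**Conclusion.** The concern holds in a limited form. The available text gives no cause-independent adverse event definition, directs follow-up to symptoms attributed to the drug, places hospitalization inside a severity grade, and uses *serious* for withdrawal without defining it. Complete and comparable capture of all adverse events in the two arms is therefore not assured, and two assessors could classify the same event differently.

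No numerical size can be given. The documents state no expected adverse event rate and no basis for estimating how many events would be missed or misgraded. A reader might try to size the problem from the 25 patients per arm, through an upper confidence bound or the weight of one event. Such figures reflect arm size alone and would be the same under perfect definitions.

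The primary hemoglobin and transfusion comparison is not affected. The safety objective counts side effects that lead to withdrawal, so it does not use the mild-to-severe grade directly; it is exposed through the undefined terms and the causality judgement. The change should be made before enrollment, but it does not threaten the main result. The conclusion assumes that staff work from 6.2.2 as written and that no fuller definition exists in the unavailable attachments.

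**What to change.** - In 6.2.2, define an adverse event as any untoward medical occurrence after first dose, whatever its cause. Keep the seven listed effects as solicited items, align 3.3.1, and reword the collection sentence so that all new events are recorded first and relatedness is assessed afterwards.
- Record severity and seriousness as two separate fields. Take hospitalization out of the severity scale and write out the seriousness criteria in 6.2.2.
- State that admissions for anemia or GI bleeding count as the secondary outcome and are tabulated separately for safety.
- Reconcile 6.2.2 and 6.3.6 on one defined term. Which events should lead to withdrawal is a clinical decision for the investigators, and no rule is proposed here.

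The cost is protocol and case report form wording, plus slightly more event recording in 50 patients. Sample size, visits and the primary analysis do not change.

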**6.2.3 Pharmacokinetics (if applicable)**

The bioavailability of oral TXA is 30-50% of the ingested dose and is not affected by food intake. Urinary excretion is the primary means of TXA elimination with 95% of an administered dose being processed by the renal system. The half-life of IV TXA was found to be 2 hours with the mean terminal half-life as approximately 11 hours

**6.3 Study Procedures****6.3.1 Informed Consent**

Each patient that meets inclusion/exclusion criteria will be asked to fill out and sign the informed consent statement. A copy is attached for reference.

**6.3.2 Screening**

All newly diagnosed Adult patients with intestinal angioectasias following at the LSU Health Network GI Clinic who meet screening criteria will be considered for inclusion. Existing patients with intestinal angioectasias that are currently not using TXA may also be approached for study participation.

**6.3.3 Recruitment, Enrollment and Retention**

The patients who meet screening protocol will be called via telephone or video call and asked to participate in the study. Patients will have an initial meeting with research study staff where all questions will be answered. Demographics will be obtained, informed consent will be signed and patient will be enrolled in study. Once enrolled, baseline lab work as previously stated will be collected for the study.

**6.3.4 On Study Visits**

Research study participants will meet for a screening and consent visit. At this time, inclusion/exclusion criteria will be review and if meet then they will be consented for the study. Following, demographic information will be collected, and baseline lab work will be done prior to the start of the interventional portion of the study.

**6.3.5 End of Study and Follow-up**

At the end of the interventional 3-month period of the study, patients will have any exit visit with the research staff. At this time, they will fill out a final patient questionnaire (see appendix).

Patient will have another follow up interview at the 6-month period (3 months following the end of the interventional portion of the study) to conclude the study.

### **6.3.6 Removal of subjects**

- At the time of consent, participants will be informed that their participation in this research study is voluntary and they may discontinue participation without penalty at any time.
- Subjects will be withdrawn from the study by the investigator if they are to have serious adverse reactions to TXA or to protect the subjects from excessive risk due to lack of benefit demonstrated by TXA.
- Data collection prior to participant withdrawal may be retained and used in a manner that is consistent with study design and purpose unless participant expresses that their information to not used in the study

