## **6.4 Statistical Method**

### **6.4.1 Sample Size Considerations**

We based our sample size estimate on assumptions for our primary aim, as this is the most important aim for providing information to support future recommendations with regards to TXA in patients with intestinal AE. A total of 50 subjects will be enrolled with 1:1 randomization to either TXA or placebo. For the primary study endpoint of hemoglobin, we will have 80% power to detect an average increase of 25% from baseline to 3 months between TXA and placebo groups ( $\alpha = 0.05$ ). We expect 75% of patients on TXA to have a 2 gm/dl improvement in overall hemoglobin while only 25% in placebo group see a 2gm/dl improvement. We expect 75% of TXA patients to require zero blood transfusions compared to placebo group requiring 1 blood transfusion on average per patient over 3 months.

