### **6.4.2 Planned Analyses**

We will characterize subjects with regard to baseline and follow up hemoglobin/hematocrit (H/H) and other endpoints previously described. We will summarize demographics and other predictors of clinical status. Continuous variables will be summarized by mean, standard deviation and range as appropriate. The primary analysis will compare the absolute and percent change in hemoglobin with adjustment for baseline in linear regression models. Using multivariable logistic regression models adjusting for baseline hemoglobin, we will assess if the odds of achieving a clinically relevant improvement in hemoglobin differs by treatment assignment. The secondary outcomes will be analyzed similarly using linear regression models adjusting for baseline values.

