### 7.3 Deviations/Unanticipated Problems

We will attempt to minimize missing data; however, we have planned for its occurrence. For subjects lost to follow-up, we will use all of the information available until the end of follow-up. This protocol will continue to follow subjects and perform lab tests even if a subject drops-out from the treatment portion of the study. If a subject decides that he/she does not wish to continue taking the study drug, the subject will stop the investigational treatment, but will still be strongly encouraged to continue to follow-up with the study personnel for all scheduled study follow ups (e.g., lab draws and symptom reporting), so that missing data will be minimized.

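### Sections 6.3.6 and 7.3 do not settle whether CBCs continue after investigator withdrawal, and the primary regression has no method for a month-3 Hb lost for an outcome-related reason.

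*Combined protocol and SAP*

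**What the plan says.** **Withdrawal (6.3.6).** "Subjects will be withdrawn from the study by the investigator" in two situations: serious adverse reactions, or "to protect the subjects from excessive risk due to lack of benefit demonstrated by TXA". No Hb threshold or timing is given for the second. The next bullet says "Data collection prior to participant withdrawal may be retained and used in a manner that is consistent with study design and purpose", unless the participant objects. It does not mention data after withdrawal.

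**Follow-up (7.3).** "This protocol will continue to follow subjects and perform lab tests even if a subject drops-out from the treatment portion of the study". The detailed instruction to stop drug but keep attending for laboratory draws opens with "If a subject decides that he/she does not wish to continue taking the study drug". For subjects lost to follow-up, "we will use all of the information available until the end of follow-up".

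**Analysis (6.4.1 to 6.4.3).** The primary analysis will "compare the absolute and percent change in hemoglobin with adjustment for baseline in linear regression models". Section 6.4.2 names no time point and no analysis set. Month 3 is implied by the sample-size text, which refers to "an average increase of 25% from baseline to 3 months between TXA and placebo groups". Section 6.4.3 says only that missing data will be noted and discussed. CBCs are scheduled at baseline and at months 1, 2 and 3 (5.1).

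**The concern.** Leaving the study and leaving treatment are different events. Section 6.3.6 describes the first and 7.3 the second, and neither says which applies when the investigator takes a patient out. Site staff could follow either one.

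This matters because lack of benefit is judged on much the same information as the primary outcome. A patient whose Hb is falling at month 2 is a natural candidate for withdrawal and would probably have had a poor month-3 value. If that value is not collected, it is not missing at random with respect to a regression that uses only baseline and month 3.

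A single regression on change drops such a patient unless a rule is added. The promise in 7.3 to use all available information is a principle, not an estimator. The choice among completers only, last available value and a repeated-measures model could therefore be made after the data are seen, and these do not give the same answer. With 25 patients per arm, a few selective losses count.

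**Working it through.** **1. The plan's own figure.** Section 6.4.1 claims 80% power with 50 patients at alpha 0.05. It gives no SD and no baseline Hb, so the figure cannot be reproduced. It can be inverted (two-sided test assumed):

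- Detectable standardized difference = (1.960 + 0.842) × √(2/25) = 0.792.
- At an assumed baseline Hb of 8 g/dL, a 25% increase is 2.0 g/dL, so the implied SD is 2.0 / 0.792 = 2.52 g/dL. Assumed baselines of 7 to 10 g/dL give SDs of about 2.2 to 3.2.

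**2. Assumed inputs for the illustration.** None of these is in the documents except 25 per arm (6.1.2).

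- Mean change at month 3: placebo +1, TXA +3 g/dL (true difference 2.0), accruing linearly, so +0.67 and +2.00 at month 2.
- SD of change 2.52; correlation between months 2 and 3 of 0.8.
- Month 3 is missing if the month-2 change is below a cut-off c of −3, −2 or −1.5 g/dL, with the same rule in both arms.

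**3. Expected bias of a completers-only fit.** For each arm let a = (c − month-2 mean) / 2.52. The proportion withdrawn is Φ(a). The completers' month-3 mean is too high by 0.8 × 2.52 × φ(a) / (1 − Φ(a)).

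| c | Placebo withdrawn; shift | TXA withdrawn; shift | Completer difference | Understated by |
|---|---|---|---|---|
| −3 | 7.3%; +0.301 | 2.4%; +0.115 | 2.0 + 0.115 − 0.301 = 1.81 | 9.3% |
| −2 | 14.5%; +0.537 | 5.6%; +0.242 | 2.0 + 0.242 − 0.537 = 1.70 | 14.7% |
| −1.5 | 19.5%; +0.690 | 8.2%; +0.334 | 2.0 + 0.334 − 0.690 = 1.64 | 17.8% |

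More placebo patients are lost, and those lost are the worst, so the placebo mean rises more than the TXA mean.

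**4. Simulation at 25 per arm.** Simulated trials with the assumed difference, SD, correlation and cut-offs gave an understatement of about 9–17%, in line with the formula, and power falling from about 79% with complete data to 65–72%. A check run with exactly the means above gave 73%, 69% and 65% at the three cut-offs. Part of the power loss comes from the smaller estimate and part from fewer patients. Carrying the last value forward erred slightly the other way (2.04 to 2.06). A fit that uses month-2 Hb stayed within about 2% of the true value.

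**5. Limits of step 4.** The good recovery is built in, because loss was made to depend only on observed Hb. In a separate run with a true difference of 3.33 g/dL and loss driven by the unseen month-3 value, a model using months 1 and 2 gave 3.18, 3.02 and 2.96, which leaves about 5–11% of the effect missing. Completers only gave 2.93, 2.63 and 2.47.

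**The case against.** **Section 7.3 may already settle the follow-up question.** Its general sentence about continuing tests does not limit who initiates stopping, and the later sentence about a subject's own decision may be only an example. The retention bullet in 6.3.6 may concern only voluntary leavers. This stands as a possible reading. It would be wrong to infer that CBCs stop after every investigator withdrawal. What remains is that 6.3.6 speaks of the study and 7.3 of treatment. If 7.3 does govern, little of this loss occurs and one sentence settles that part.

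**The plan does not commit to completers only.** Using all available information sits poorly with discarding month-1 and month-2 Hb. That is fair, although 7.3 says it of subjects lost to follow-up and does not say that withdrawn subjects count as such. The completers-only fit is what a regression on change does by default, not something the plan declares. A named method is still missing, and continued CBCs would not remove the need for one: participants may leave at any time, and 7.3 itself expects loss to follow-up.

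**Bias in favor of TXA.** Because the lack-of-benefit wording names TXA, a reader might infer that mainly TXA patients would be withdrawn, which would inflate the effect and the false-positive rate. The documents do not support this. It needs withdrawal that differs by arm, and 6.1.3 describes identical bottles intended to keep participants and the research team free of bias. With the same rule in both arms and no true effect, simulated false-positive rates were 4.6–5.3%.

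**The size is assumed.** This stands in full. Transfusions are a particular gap: 6.4.1 expects one per placebo patient on average, and they would change both observed Hb and apparent benefit.

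**Conclusion.** The point holds in a limited form. The text leaves open whether scheduled CBCs continue after investigator withdrawal, one withdrawal trigger is related to the outcome, and no method is named for a missing month-3 Hb.

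If withdrawal is applied alike in both arms without knowledge of arm, the likely direction for a completers-only fit is understatement of the TXA effect with loss of power. The 9–17% and the fall in power to 65–72% are illustrations. They rest on an assumed difference of 2.0 g/dL, SD 2.52, correlation 0.8, a month-2 fall of 1.5 to 3 g/dL as the trigger, and no transfusions. They should not be read as an estimate for this trial.

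This should be changed before data are seen. It does not make the trial invalid, and confidence in the size is no more than moderate.

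**What to change.** 1. **Reconcile 6.3.6 and 7.3.** State whether scheduled CBCs and follow-up continue after any withdrawal, whoever initiates it. This need not change who stops drug or when.
2. **Replace the primary analysis in 6.4.2 and 6.4.3.** Use a repeated-measures mixed model of Hb at months 1, 2 and 3, with arm, month, arm-by-month and baseline Hb, and an unstructured covariance. Include all randomized patients as assigned, with the month-3 contrast as primary. State how the percent-change and responder analyses handle the same missing values.
3. **Report withdrawals by arm and reason, with one sensitivity analysis.** For example, lower the modelled month-3 Hb of withdrawn patients by a fixed amount. This is needed because the mixed model corrects only for loss explained by observed Hb.

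The cost is a few sentences of protocol text and slightly more analysis work. The CBCs at months 1 to 3 are already scheduled, so no visits or patients are added.

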#### 6.1.3 Packaging/Labelling

Both TXA and placebo will be packaged in identical bottles with similar labeling so participants and the research team will not be affected by bias.

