### 7.6 Study Discontinuation

Reasons for discontinuing the study include futility, adverse events (harm), early evidence of superiority of one intervention (benefit) and insufficient recruitment (a cut-off at 80% of the planned sample size).

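### Section 6.3.6 has the investigator withdraw subjects from the study where it should only stop study drug, which sits badly with the continued follow-up in 7.3

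*Combined protocol and SAP*

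**What the plan says.** The second bullet of 6.3.6 (Removal of subjects) is mandatory. The investigator will withdraw a subject from the study for "serious adverse reactions to TXA or to protect the subjects from excessive risk due to lack of benefit demonstrated by TXA". It names no measure, threshold or time for judging lack of benefit. The third bullet deals only with earlier data: "Data collection prior to participant withdrawal may be retained and used in a manner that is consistent with study design and purpose", unless the participant objects.

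Section 7.3 says "This protocol will continue to follow subjects and perform lab tests even if a subject drops-out from the treatment portion of the study". Its next sentence gives the detailed procedure (stop the drug, encourage all scheduled follow-up) for one case: "If a subject decides that he/she does not wish to continue taking the study drug". It also says "For subjects lost to follow-up, we will use all of the information available until the end of follow-up".

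Three other places bear on the point:
- Section 6.1.3 packages TXA and placebo identically "so participants and the research team will not be affected by bias".
- The adverse-event section under 6.2.2 uses arm-neutral wording: "Each adverse event will be assessed and determine to be related or not related to the study medication".
- Section 4.3 has a secondary objective on side effects that lead to withdrawal of the drug, so the plan already treats stopping drug as an event in its own right.

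**The concern.** Stopping a drug and leaving a trial are different events. Section 7.3 keeps them apart; the removal rule in 6.3.6 does not. Site staff who turn to the section on removal of subjects find an instruction to withdraw from the study and a statement about earlier data, and nothing that tells them to keep drawing blood counts or recording events.

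Two things are at stake. The first is safety. A subject taken off for a serious reaction, possibly a thromboembolic event, is the one whose later course most needs recording. The second is the primary comparison. If lack of benefit is judged on an individual's hemoglobin or transfusions, the subjects removed are those doing badly, and their month-3 values are missing for that reason. Section 6.4.3 says only that missing data would be noted and discussed, and 6.4.2 does not say how withdrawn subjects enter the regression.

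**Working it through.** **Comparing the sections.** The point rests on wording, not on a figure in the plan.

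| Question | 6.3.6, second and third bullets | 7.3 |
|---|---|---|
| Who decides? | Investigator | General sentence: not stated. Detailed case: the subject |
| What ends? | Participation in the study | Treatment only |
| Later labs and follow-up? | Not mentioned | Continue |
| Which data are used? | Those from before withdrawal | All available up to the end of follow-up |
| Term for the drug | TXA | Study drug |

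The general sentence in 7.3 is broad enough to include investigator stops, but it covers leaving the treatment portion. A subject withdrawn from the study has left more than that. The two sections can be reconciled only by reading the action in 6.3.6 as stopping drug, which it does not say.

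**Direction of bias, for illustration only.** Every input except the planned 25 per arm is an assumption: month-2 and month-3 values with SD 1, a true effect of 0.8 SD at both months, correlation r = 0.7 between the months, removal in either arm when the month-2 value is below a common cutoff c, and month 3 then not collected. The expected month-3 mean among those who stay, in an arm with mean m, is

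m + r × φ(c − m) / [1 − Φ(c − m)].

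With no true effect, m is the same in both arms, the added terms cancel and the expected difference is 0. With a true effect, placebo loses more low values, so its mean rises more:

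- 4% of placebo removed (c = −1.751). Placebo: 0.7 × 0.0862/0.960 = 0.063. TXA: 0.8 + 0.7 × 0.0154/0.995 = 0.811. Difference about 0.75 SD.
- 10% removed (c = −1.282). Placebo: 0.7 × 0.1755/0.900 = 0.137. TXA: 0.8 + 0.7 × 0.0457/0.981 = 0.833. Difference about 0.70 SD.
- 30% removed (c = −0.524). Placebo: 0.7 × 0.3477/0.700 = 0.348. TXA: 0.8 + 0.7 × 0.1660/0.907 = 0.928. Difference about 0.58 SD.

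These are unadjusted. Section 6.4.2 plans linear regression adjusted for baseline. In simulation, with an assumed correlation of 0.5 between baseline and both later values, the completer estimates become about 0.77, 0.73 and 0.65 SD. The bias is smaller and in the same direction. The 4% row removes about 1 of 50 subjects in total and is the closest to rare use.

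**Dilution under the fix.** About 0.5%, 1.9% and 9.3% of the TXA arm would be stopped in the three rows. In the worst case each loses the whole effect by month 3, and the estimate falls by that share of 0.8 SD: 0.8 × (1 − 0.005) = 0.80, 0.8 × (1 − 0.019) = 0.78 and 0.8 × (1 − 0.093) = 0.73 SD.

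**The case against.** The best reply is that 7.3 already settles the matter. Its general sentence is not limited by who decides, the case of the subject's own decision can be read as one example, and the third bullet of 6.3.6 concerns permission to keep data; it does not forbid further follow-up. Much of this stands. 7.3 may well have been meant to cover investigator stops, so it would go too far to say that the plan prohibits follow-up after removal. What remains is an operative instruction in 6.3.6 that says something else.

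The bias also needs several steps that the text does not supply: a per-patient judgement, made on hemoglobin, with month 3 then not collected and an analysis of completers. Lack of benefit shown by TXA could instead mean a trial-level finding, close to the futility reason in 7.6, although it stands in a rule about individual subjects. On that reading the bias argument falls away, while the safety argument remains for serious reactions. The stated aim of protecting subjects from excessive risk also suggests rare use. Finally, an analysis that uses the observed month-2 count would largely avoid the bias: under the assumptions above it recovers 0.80 SD. Section 7.3 would allow such an analysis, but 6.4.2 does not specify one.

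A reader might infer from the TXA wording that the rule breaks the masking, or applies in one arm only and so inflates type I error. The documents do not support that. No section provides for unblinding, and 6.2.2 already has events judged against the study medication. The practical reading is both arms alike, under which the expected difference is zero when there is no effect.

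**Conclusion.** The point holds as a minor one. The action required by 6.3.6 does not match the follow-up intended in 7.3. Taken literally, it ends safety follow-up after a serious reaction, and it may lose primary-outcome data for reasons tied to the outcome. The safety part needs no statistical assumption. The bias part depends on a per-patient reading of lack of benefit and on month-3 data not being collected. Its direction is toward no effect, and it is small if the rule is used rarely.

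It is tempting to turn the illustration into a stated loss of power for this trial. The documents do not support that: they give no withdrawal rate and no correlation between visits, and the unadjusted figures overstate the bias, under the assumed baseline correlation, relative to the baseline-adjusted model that is planned.

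**What to change.** - In the second bullet of 6.3.6, change the action from withdrawal from the study to stopping study drug. State that blood counts and transfusion, hospitalization and adverse-event follow-up continue to month 3 unless the subject withdraws consent.
- In 7.3, add one sentence saying that continued follow-up applies to stops decided by the investigator as well as by the subject.
- In the same bullet, write study drug in place of TXA. This is editorial alignment with 6.2.2 and 7.3 and changes no procedure.

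The clinical criteria for stopping stay with the sponsor, and a subject's right to leave under the first bullet is untouched.

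The cost is a few words and one sentence. The month-3 count is already scheduled (5.1), so no visit or test is added. The downside is that month-3 values from subjects off drug slightly dilute the treatment contrast. The benefit is observed outcome and safety data in place of missing data. It is not a gain in power over an analysis that uses the month-2 count.
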